8.4 Randomization Criteria

In order to be randomized, a subject **MUST** meet the following criteria:

1. Underwent an eligible surgery (Inclusion Criterion #4)
2. NGT tube has been removed, if inserted intraoperatively
3. Is able to receive oral medications

Additionally, in order to be randomized, a subject **MUST NOT** have achieved both upper and lower GI components that comprise the primary efficacy endpoint **before Day 1 Randomization**, as listed below:

Upper GI

4. Transitioned from clear liquids to full liquids and/or solid food

Lower GI

5. Had first BM

OR

Achieved all 3 events below:

- a) Absence of abdominal distension; AND
- b) Experienced first flatus after surgery; AND
- c) Presence of bowel sounds after surgery

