10.2.1.2 Intraoperative Elements

- Excess fluid administration and volume overload should be avoided.
- Transverse abdominis plane (TAP) blocks (with bupivacaine or bupivacaine liposome injectable) are permitted.
- Epidural anesthesia should not be used for the purposes of this protocol in order to reduce confounding of the effect of TU-100 on the primary outcome measure.

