14.2 Determination of Sample Size

The study is expected to enroll approximately 402 eligible subjects (with expected loss to follow-up or censorship of primary endpoint) with 1:1:1 randomization ratio over a post-surgery period (up to 10 days). The study is sized to achieve approximately 87% power to detect a hazard ratio (HR; TU-100 versus placebo) of 1.428 for GIR, which translates into an improvement in median time to GIR from 48 hours (2.0 days) for placebo (reference) to 34 hours (1.4 days) for TU-100 at a 0.05 significance level of one-sided log-ranked test for equality of time to GIR survival curve.

Based on historical evidence, it is assumed that a small proportion of subjects will be lost to follow-up or will have events censored due to required analytical methods. To account for this anticipated loss in contribution of events to the primary endpoint, an additional 36 subjects (approximately 10% of 366) will be enrolled to achieve a final sample size of 402 subjects (134 per group).

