14.5.2 Analysis of Primary Efficacy Endpoint

The primary efficacy variable is time to gastrointestinal recovery (TGIR), a composite endpoint defined as the following:

TGIR = maximum (time to first toleration of liquids; time to first BM OR [absence of distention AND bowel sounds AND flatus])

Time to an event is defined as the elapsed time, in hours, from the end of surgery to the time of the first event, to be calculated as:

$$\text{Time to event (hours)} = (\text{time of the event} - \text{time of end of surgery})$$

When TGIR is greater than 10 days (240 hours), it will be censored at 10 days. Censoring rules for other secondary time-event endpoints will be discussed in the SAP.

The primary analysis of TGIR will be based on the Cox proportional hazard model (Cox PH) that includes the main effects for treatment and surgical approach (open versus laparoscopic). The estimates of time to event for the quartiles (25%, 50%, 75%), hazard ratios and their corresponding one-sided 95% confidence intervals (CIs), the Wald Chi-square one-sided *P* values from the Cox analysis will be summarized. The ties in the data will be handled by the Breslow method.

A secondary analysis will be applied for TGIR using the Cox PH model including main effects for treatment, surgical approach (open versus laparoscopic), and covariates such as surgical type, gender, age (years), post-operation opioid consumption (mg morphine equivalents; [APPENDIX 2](#)), thoracic epidural use, and surgery duration (hours). Backward method will be used to select statistically significant covariates (*P* < 0.1). Adjusted *P* value and HR will be provided after the final model is selected.

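### The primary Cox model adjusts only for surgical approach; pre-specifying the sponsor's own baseline covariates could add power, although the stated 87% stands

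*Combined protocol and SAP*

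**What the plan says.** Section 14.5.2 specifies the primary model as a Cox model "that includes the main effects for treatment and surgical approach (open versus laparoscopic"). Approach is also the only randomisation stratum (Section 9.3.1).

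A secondary Cox model in the same section adds an open-ended list: surgical type, gender, age, postoperative opioid consumption in morphine equivalents, thoracic epidural use and surgery duration. For this model, "Backward method will be used to select statistically significant covariates" at P < 0.1, and the adjusted hazard ratio and P value come from whatever model remains. Section 14.5.2 also allows further covariates to be explored and leaves sensitivity analyses to the SAP.

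Other sections bear on that list:
- Randomisation takes place on postoperative Day 1 (Sections 7.1 and 9.3.1), after surgery. Surgical type, gender, age and surgery duration are therefore fixed by then. Surgery start and stop times (Section 11.1) and demographics (Section 12.1) are collected.
- On epidurals, Section 10.2.1.2 says: "Epidural anesthesia should not be used for the purposes of this protocol".
- Section 8.4 requires that a subject must not "have achieved both upper and lower GI components that comprise the primary efficacy endpoint" before randomisation. A subject with one component already met can still enter.

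**The concern.** When outcome depends on baseline characteristics, a Cox model that includes them has more power to detect a treatment effect than one that leaves them out. Eligibility here runs from small bowel resection to total colectomy and low anterior resection (Section 8.1), and the sponsor itself lists four pre-randomisation covariates as candidates. The primary model uses none of them.

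The only planned adjusted result comes from a model chosen by looking at the data, so its P value takes no account of the selection. Two of its candidate terms are also poorly suited. Thoracic epidural use should be nearly constant under Section 10.2.1.2. Postoperative opioid consumption accrues largely after randomisation and may be affected by treatment, so adjusting for it could remove or distort part of the effect being estimated.

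At stake are some power in the primary comparison and the interpretability of the adjusted estimate.

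**Working it through.** **1. Reproduce the planned power.** Section 14.2 states: "The study is sized to achieve approximately 87% power to detect a hazard ratio (HR; TU-100 versus placebo) of 1.428 for GIR", "at a 0.05 significance level of one-sided log-ranked test for equality of time to GIR survival curve". The medians move "from 48 hours (2.0 days) for placebo (reference) to 34 hours (1.4 days) for TU-100"; 48/34 = 1.412 and 2.0/1.4 = 1.429, so 1.428 agrees with the rounded days. On numbers, "an additional 36 subjects (approximately 10% of 366) will be enrolled to achieve a final sample size of 402 subjects (134 per group"). Then 366/3 = 122 per arm, and 2 × 122 = 244 contributing subjects per dose-versus-placebo pair, taken as events.

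Schoenfeld: power = Φ(√(244 × 0.25) × ln 1.428 − 1.645) = Φ(7.810 × 0.3563 − 1.645) = Φ(1.138) = 87.2%.

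Freedman: Φ(√244 × 0.428/2.428 − 1.645) = 86.6%.

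The stated figure reproduces, and no covariate enters it. With 1.412 in place of 1.428, Schoenfeld gives 85.3%.

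**2. Compare the two models by simulation.** One dose against placebo was simulated with 134 per arm, the 240-hour cap of Section 14.5.2 and a one-sided Wald test at 0.05. There were 2,000 data sets per setting, with both models fitted to each.

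The log hazard was ln(HR) × treatment − 0.4 × open + (SD/2) × (Z1 + Z2 + Z3 + Z4), where the Z are independent standard normal covariates, so the prognostic score has standard deviation SD. The following are assumptions that the documents do not supply: exponential times, 35% open surgery, the −0.4 effect of open surgery, about 9% early censoring, and every value of SD. A score SD of 0.3 means that one SD multiplies the hazard by 1.35; for 0.5 the factor is 1.65.

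*Case A: 1.428 is the hazard ratio conditional on the covariates.*

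| Score SD | Approach-only HR | Approach-only power | Adjusted power | Gain (points) |
|---|---|---|---|---|
| 0 | 1.43 | 85.0% | 84.8% | −0.2 |
| 0.2 | 1.41 | 83.2% | 84.7% | 1.5 |
| 0.3 | 1.40 | 80.8% | 84.1% | 3.3 |
| 0.5 | 1.36 | 75.0% | 84.4% | 9.4 |
| 0.75 | 1.31 | 64.7% | 83.6% | 18.9 |
| 1.0 | 1.27 | 55.7% | 83.0% | 27.3 |

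*Case B: 1.428 is the hazard ratio the approach-only model estimates.* The conditional hazard ratio was calibrated to achieve this.

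| Score SD | Conditional HR | Approach-only power | Adjusted power | Gain (points) |
|---|---|---|---|---|
| 0.3 | 1.465 | 85.1% | 89.2% | 4.1 |
| 0.5 | 1.522 | 85.7% | 94.1% | 8.4 |
| 0.75 | 1.613 | 85.2% | 97.3% | 12.1 |

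Under no treatment effect (SD 0.5), type I error was 4.5% approach-only and 4.8% adjusted. Monte Carlo standard errors are √(0.85 × 0.15/2000) = 0.8 points for power near 85% and √(0.05 × 0.95/2000) = 0.5 points for type I error. The 85.0% at SD 0 lies a little below the 87.2% from the formula, which is an approximation; the comparison of interest is between the two models.

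**3. A second set of assumptions.** A separate simulation took conditional HR 1.428, 10% dropout, covariate log hazard ratios of 0.15 to 0.45 in absolute size, and one recovery component already met in 40%. Approach-only against fixed adjustment gave 79% against 87% at those strengths, 83.7% against 85.4% at half of them, and 86.2% against 86.5% with no prognostic effect. Type I error was 5.0% against 5.4% (4,000 runs, SE 0.35).

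**4. Component status at randomisation.** The endpoint is the later of the upper and lower recovery times, so a subject who enters with one met needs only the other. Simulating the two components directly (2,500 runs, assumed distributions), stratifying by status raised power from 86.4% to 89.0% in one setting and from 90.9% to 91.4% in another: gains of 2.6 and 0.5 points.

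**The case against.** The strongest reply is that nothing is lost against the plan. Section 14.2 takes its hazard ratio from arm medians and sizes the trial on a log-rank test with no covariates mentioned. Case B is the reading closest to that, and there the approach-only power stays at 85.1% to 85.7% whatever the prognostic strength. This stands. A reader might infer from Case A that the trial falls short of 87%; the documents do not support that, because the shortfall arises only when 1.428 is taken as the covariate-conditional value.

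A reader might also infer that the primary hazard ratio is biased toward 1. It is not. The approach-only and adjusted hazard ratios are different quantities (non-collapsibility), and the primary test holds its level. Nor do the documents call the four covariates known predictors: they are candidates for a screen, and the gain may be nil.

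It is fair to add that the backward-selected model is labelled secondary and its selection rule is stated in advance. Section 14.1 gives the SAP precedence over the protocol, and covariate handling fixed there would govern. The epidural term is minor, since Section 14.7 tabulates epidural use anyway and a near-empty term does little harm in a secondary model.

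Finally, component status cannot be assumed to be on file. Section 8.4 can be satisfied by finding either component unmet, and the eDiary is handed out only after randomisation (Section 10.2.3).

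What remains is that four covariates fixed before randomisation are left to data-driven selection, when using them in advance gains power if they matter and costs essentially nothing if they do not.

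**Conclusion.** The point holds as a missed gain in efficiency, not as an error. The primary test is valid and the stated 87% power is not contradicted. Fixed adjustment for surgical type, gender, age and surgery duration would change power by essentially nothing if they are not prognostic (85.0% against 84.8%). It would add about 3 to 4 points at score SD 0.3 and 8 to 9 points at SD 0.5, under either reading of 1.428, with type I error near 5%. Larger gains need stronger covariates than there is any basis in the documents to assume.

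These sizes rest on assumed prognostic strengths, exponential times and four independent normal covariates. The direction does not depend on which reading of 1.428 is taken. The unsuitability of opioid consumption and epidural use as adjustment terms follows from the protocol's own text and timing and needs no simulation.

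**What to change.** In Section 14.5.2 and the SAP, before unblinding:

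- Make the primary model a Cox model with treatment, surgical approach, surgical type, gender, age and surgery duration as fixed, pre-specified covariates, with no variable selection. State how each is coded.
- Keep the approach-only model as a sensitivity analysis.
- Delete the backward step. Remove thoracic epidural use and postoperative opioid consumption from the adjusted model; both can still be summarised descriptively, as Sections 14.7 and 14.6.3 already plan.
- Add component status at randomisation (none, upper only, lower only) only if the eCRF records each component separately before randomisation. Confirm this first; the simulated gain was modest.

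The four covariates need no extra subjects or assessments, so for them the cost is protocol and SAP wording. The downside is that the reported hazard ratio becomes conditional on the listed covariates and is no longer the same quantity as the one implied by the medians in Section 14.2. The plan should say so.

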11.2 Gastrointestinal Assessments

Gastrointestinal assessments will be performed twice daily in the morning and afternoon, starting on randomization Day 1, and continuing until hospital discharge or study termination.

Assessments must be separated by at least 6 hours. Gastrointestinal assessments will include:

- Recording time of first:
 - Clear liquid toleration (i.e., time at which the subject transitions from clear liquids to the next diet stage [full liquids or solids])
 - Solid diet toleration (i.e., able to eat a meal that requires chewing without a vomiting episode by the time the next consecutive meal is offered)
 - Note, if the first solid meal is consumed on the day of hospitalization (i.e., the day of surgery), the time to toleration of solids is as stated (e.g., the time to eat solids without a vomiting episode by the time the next consecutive meal is offered). Further, if the first solid meal is consumed on the day of discharge, the time to toleration of solids criteria is met if there is no vomiting prior to discharge. In all cases, the actual time that should be recorded on the eCRF is the time the meal was consumed by the subject, not the cutoff time for vomiting prior to next consecutive meal or discharge.
 - Absence of distention + presence of bowel sounds + flatus (time of when all 3 conditions have been achieved)
- Record time subject is ready for hospital discharge (based solely upon recovery of GI function as determined by the treating medical team)

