14.5.3 Analyses of Secondary and Exploratory Efficacy Endpoints

Similar analysis for the primary efficacy endpoint will be applied for other time to event efficacy endpoints.

A secondary efficacy variable, time to ready for discharge (based solely on the treating medical team's determination of GI recovery), which is defined as the time to the assessment date of "ready for hospital discharge." Length of stay is based on the time to the calendar day of discharge order written from the calendar day of surgery.

Treatment effect on other numeric variables will be analyzed using an ANOVA if normally distributed, or the Wilcoxon rank sum test otherwise. Treatment effect on categorical variables will be analyzed using the stratified Miettinen and Nurminen (M&N) method (stratified by surgical approach) ([Miettinen 1985](#)), or the logistic regression model if appropriate. Potential covariates will be identified and tested.

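### If length of stay, a whole-day count, is analysed by Cox regression, the Breslow tie rule shrinks its hazard ratio toward 1; Efron ties avoid this at no cost

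*Combined protocol and SAP*

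**What the plan says.** Section 14.5.2 and the synopsis make a Cox model with treatment and surgical approach the primary analysis of time to GI recovery. The rule for tied times is: "The ties in the data will be handled by the Breslow method". Time for that endpoint is "the elapsed time, in hours, from the end of surgery to the time of the first event".

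Section 14.5.3 extends the method: "Similar analysis for the primary efficacy endpoint will be applied for other time to event efficacy endpoints". Section 14.5.2 does the same for the stratified log-rank test, the Kaplan-Meier estimates and restricted mean survival time. No other tie rule appears.

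Two secondary endpoints are described in days in Section 14.5.3:

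- Length of stay: "Length of stay is based on the time to the calendar day of discharge order written from the calendar day of surgery". Section 6.2.2 also bases it on the calendar day.
- Time to ready for discharge, "which is defined as the time to the assessment date of" readiness. The data-collection instruction in Section 11.2 is different: "Record time subject is ready for hospital discharge". Section 10.2.3 likewise asks for a time.

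The same section has a second route for non-survival data: "Treatment effect on other numeric variables will be analyzed using an ANOVA if normally distributed, or the Wilcoxon rank sum test otherwise". It does not say which route length of stay takes.

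**The concern.** Breslow's approximation is harmless when ties are rare and poor when many events share one time. A stay counted in whole days puts up to 134 subjects per arm on a handful of values, so heavy ties follow from the definition.

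Length of stay is the one outcome named in the first secondary objective (Section 6.1.2). If it goes through the Cox model as written, the reported hazard ratio, its confidence limit and the Wald P value would all understate a real effect. In a Phase 2 trial, where the size of the effect informs what is done next, that is an avoidable estimation error.

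**Working it through.** **Inputs from the documents.** Hazard ratio 1.428, one-sided 0.05, about 87% power, 366 subjects before inflation (122 per arm) and 402 after (134 per arm), all from Section 14.2. Censoring of the primary endpoint at 240 hours is from Section 14.5.2.

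**The plan's own figure.** For one dose against placebo, with d = 244 events and equal allocation, Schoenfeld's formula is

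power = Φ(√(d × 0.5 × 0.5) × ln HR − z)

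= Φ(√61 × ln 1.428 − 1.645) = Φ(7.810 × 0.3563 − 1.645) = Φ(1.138) = 0.872.

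The stated 87% reproduces. It is for GIR; no power is stated for any secondary endpoint.

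**Why ties matter.** At an event time with n1 and n0 at risk (n in total) and d events, d1 of them on active and d0 on placebo:

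- Breslow uses the denominator (n0 + n1·e^β) for all d events, as if nobody left the risk set during the day.
- Efron uses, for k = 0 to d − 1, (n0 − (k/d)·d0) + (n1 − (k/d)·d1)·e^β, which removes the tied subjects gradually.

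At β = 0 the Breslow information is d·n1·n0/n². The hypergeometric variance used by the log-rank test is that value times (n − d)/(n − 1). As an illustration, if 30 of 90 remaining subjects leave on one day, the factor is 60/89 = 0.67. Breslow therefore overstates the null variance on such days, and its Wald test rejects too seldom.

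**Simulation.** 122 per arm, proportional hazards, times rounded up to a grid, censored at 10 days, two-arm Cox model without the surgical-approach term, one-sided Wald test at 0.05. There were 2,000 trials per scenario (1,000 for the 1-hour grid). The documents give no stay distribution, so these are assumptions:

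- A: 1 day plus Weibull shape 2, placebo median 4 days.
- B: 1 day plus Weibull shape 1.2, placebo median 4 days.
- C: 2 days plus Weibull shape 1.5, placebo median 3.5 days.
- D: exponential, placebo median 48 hours.
- E and F: as D, on 12-hour and 1-hour grids.
- G: 1 day plus Weibull shape 1.5, placebo median 3.5 days, 12-hour grid.

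Results at true HR 1.428:

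| Scenario | Grid | Share of events on busiest time | Breslow HR / power | Efron HR / power | Log-rank power | Efron minus Breslow power |
|---|---|---|---|---|---|---|
| A | 1 day | 26% | 1.317 / 0.727 | 1.416 / 0.856 | 0.852 | 0.129 |
| B | 1 day | 23% | 1.357 / 0.778 | 1.425 / 0.853 | 0.854 | 0.075 |
| C | 1 day | 38% | 1.268 / 0.600 | 1.395 / 0.820 | 0.836 | 0.220 |
| D | 1 day | 35% | 1.341 / 0.779 | 1.431 / 0.869 | 0.871 | 0.090 |
| E | 12 h | 20% | 1.384 / 0.815 | 1.432 / 0.865 | 0.866 | 0.050 |
| G | 12 h | 15% | 1.373 / 0.811 | 1.425 / 0.854 | 0.853 | 0.043 |
| F | 1 h | 3% | 1.432 / 0.870 | 1.437 / 0.874 | 0.873 | 0.004 |

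Ungrouped times gave power 0.854 to 0.872 in scenarios A to D.

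**Hand check of scenario A.** The mean standard errors are nearly equal (0.130 and 0.131), so the loss comes from the shrunken estimate: ln 1.317 / 0.130 = 2.12 for Breslow, against ln 1.416 / 0.131 = 2.66 for Efron.

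**Under HR 1.0.** On the day grid, one-sided type I error is 0.028, 0.034, 0.017 and 0.025 (A to D) with Breslow, and 0.051 to 0.056 with Efron.

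**Other settings.** Further runs with 122 or 134 per arm and an assumed placebo median of 4 to 5 days gave Breslow HR 1.30 to 1.37, power 70% to 84% and type I error 0.015 to 0.031. Efron gave 1.41 to 1.44, 85% to 91% and about 0.05. Runs with 134 per arm and surgical approach in the model pointed the same way: Breslow 1.30 to 1.36 and 73% to 82%, Efron 1.40 to 1.43 and 87% to 88%. At a smaller true HR of 1.25, A gave Breslow 1.187 and power 0.334 against Efron 1.241 and 0.491; C gave 1.169 and 0.260 against 1.242 and 0.510.

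**The case against.** **Length of stay may never reach the Cox model.** Section 6.2.2 lists it without the time-to label its neighbours carry, and Section 14.5.3 offers ANOVA or Wilcoxon for numeric variables. This stands as an uncertainty. The time-to wording in Section 14.5.3, placed before the sentence on other numeric variables, favours Cox but does not settle it. A reader who takes the Cox route as stated goes beyond the text.

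**Ready for discharge is not a whole-day endpoint as collected.** This stands. A reader might infer from the word for date in Section 14.5.3 that both endpoints are recorded by day. Sections 10.2.3 and 11.2 call for a time, and "Gastrointestinal assessments will be performed twice daily in the morning and afternoon". On a 12-hour grid the loss is 4 to 5 points, and a finer record would lose less.

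**The plan as a whole does not lose its chance of seeing an effect on stay.** This also stands. The log-rank test does not depend on the Breslow choice and keeps 84% to 87% power on the same day-level data. Time to discharge order written is a separate secondary endpoint with date and time collected (Sections 6.2.2, 10.2.3 and 11.4). Neither, however, corrects the Cox hazard ratio and confidence limit reported for length of stay.

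**The error is conservative, no power is claimed for secondary endpoints, and the SAP may override the rule** (Section 14.1). All true, and they limit the consequence. But no separate SAP text is in the documents, so Breslow is the only rule on record, and a biased estimate remains biased whatever power was promised.

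**Conclusion.** The point holds conditionally. If length of stay is analysed by Cox with Breslow ties, the hazard ratio is pulled toward 1 and the Wald test is conservative. At a true HR of 1.428, Breslow gives about 1.27 to 1.37 with power about 60% to 84%, against Efron's 1.40 to 1.44 and 82% to 91%. The loss is roughly 5 to 22 points, and one-sided type I error is about 0.015 to 0.034 instead of 0.05. For ready for discharge this applies only if the date is used literally.

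The direction was the same in every day-level scenario. The size rests on assumed stay distributions, 10-day censoring carried over from the primary endpoint, rounding up as a stand-in for calendar days, and a hazard ratio that the plan assumes for GIR and not for stay. Simulation error is about 1 point of power in the tabulated runs.

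Two stronger readings are not supported. The primary result is not at risk: on a 1-hour grid the two methods give 0.870 and 0.874. Nor does the rule inflate false positives; it makes them rarer than nominal. This is a free improvement, not a flaw in the primary analysis.

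**What to change.** Name Efron in place of Breslow for all Cox models, in the synopsis and Section 14.5.2, so that the analyses in Section 14.5.3 inherit it (TIES=EFRON in SAS PROC PHREG). In Section 14.5.3, define time to ready for discharge from the recorded time rather than the date. It would also help to add one sentence saying whether length of stay is analysed as time-to-event or as a numeric variable.

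The cost is one word, one software option and a short clarification, made before unblinding. No data collection or sample size changes. Efron and Breslow coincide when there are no ties, so the primary analysis gives up nothing.
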